#### 3 STUDY DESIGN

This is a multi-site, two stage, open label, randomized (1:1:1) controlled trial.

Figure 2. Schematic of study design

Treatment is for 14 days from baseline. Patients will receive follow-up assessment at 7, 14 and 28 days after the first dose.

The time allowed for screening assessments allows time for eligibility assessments to be included.

- Screening Period: up to 7 days to the day randomisation
- Treatment Period: 14 days

MATIS version 4.0 dated 2nd November 2022

IRAS: 282552 Page **22** of **57** 

Imperial College Healthcare

- Follow-up period: Day 14 to 28

Patients who have recovered and are fit for discharged from hospital during the treatment period, will be discharged home with trial medication to complete a fixed 14 day course. Such patients will be followed up weekly with telephone monitoring until day 28 and additional blood test monitoring where practically possible.

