#### 3.3 STUDY ENDPOINTS

#### **Primary endpoints**

The primary endpoint is progression from mild to severe COVID-19 pneumonia within 14 days in hospitalised patients. Patients are recruited at a WHO COVID-19 Severity Score of 3 and 4 and the primary endpoint is the comparison of patients whose COVID-19 pneumonia progresses to a severity score  $\geq$  5 on the modified WHO Ordinal Scale. Specifically, the primary endpoint is met when the following are recorded within 14 days:

- Death
- Requirement for invasive ventilation
- Requirement for non-invasive ventilation including CPAP and high flow nasal oxygen
- O2 saturation < 90% on ≥60% inspired oxygen

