In Stage 2 a logistic regression model will be used to assess the treatment effect of RUX and FOS compared to SOC. The model will include the treatment arms, baseline modified WHO Severity Score, trial co-enrolment at baseline, and randomisation stratification variables viz. site and age (<65 vs ≥65). As well as reporting OR and 95% CIs, the model will be used to estimate the difference in proportion of participants with modified WHO COVID-19 Ordinal Score ≥5. The treatment effect in the absence of post-randomisation co-enrolment and receipt of rescue medication will be estimated in a supplementary analysis where participants' outcomes after either will be treated as missing and a controlled multiple imputation using a delta based approach will be used.

For the primary outcome, progression to severe COVID-19 disease within 14 days, discharge alive from the admitting hospital before 14 days will assume safety from the event (in the absence of additional data confirming otherwise). An additional sensitivity analysis will be performed if there is a change of dose after review of the first thirty patients.

For time-to-event analyses required for secondary endpoints such as time to discharge, each treatment group will be compared with SOC and modelled using a proportional hazards time-to-event model adjusted for randomisation stratification variables. Kaplan-Meier estimates for the time to event will also be plotted (with confidence intervals). The log-rank 'observed minus expected' statistic (and its variance) will be used to estimate the average event rate ratio (and its confidence interval) for those allocated to each treatment group versus the no additional treatment group.

Pre-specified subgroup analysis will be conducted for the primary outcome using the statistical test for interaction (or test for trend where appropriate) for the following: disease severity as graded by the WHO

MATIS version 4.0 dated 2nd November 2022

IRAS: 282552 Page **28** of **57** 

Imperial College Healthcare

COVID-19 Ordinal Severity Scale; time since onset of symptoms; sex; age; and comorbidities obesity, chronic heart, lung, kidney and liver disease, diabetes, immunocompromised and smoking status. Pre-specified subgroup analyses will also be conducted for the primary outcome using the statistical test for interaction (or test for trend where appropriate) for patients with admission CRP >200mg/L and/or D-dimer 2500ng/mL.

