#### 9.2 DURATION AND MODE OF FOLLOW-UP

All randomised participants are to be followed up until death, discharge from hospital or 28 days after randomisation (whichever is sooner). It is recognised that in the setting of this trial, there may be some variability in exactly how many days after randomisation, information on disease status is collected. This is acceptable and will be taken account of in the analyses and interpretation of results, the principle being that some information about post-randomisation disease status is better than none.

Where discharge occurs before 14 days, study medication will be sent home with patient. The study team will send a pre-paid envelope to the patients to return any unused medication and empty bottles if patients are not able to attend Day 14 and Day 28 visits in person.

Where discharge occurs before 28 days, patients will be invited to return weekly for monitoring of blood tests to confirm continued recovery from illness. Where this is not possible, monitoring of clinical status will be achieved by telephone.

Longer term (up to 10 years) follow-up will be sought through linkage to electronic healthcare records and medical databases including those held by NHS Digital, Public Health England and equivalent bodies, and to relevant research databases (e.g. UK Biobank, Genomics England).

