Every effort will be made to obtain follow-up data for all participants including those that stop treatment. The number and proportion of participants missing WHO COVID-19 status by treatment group and visit will be tabulated (see section 2.5 above). For participants who are discharged early the assumption will be made that they did not progress to grade 5 WHO scale. If there is a >5% rate of missing outcomes after this, we will impute missing WHO COVID-19 data in the primary analysis model using multiple imputation under the assumption of missing at random (MAR). That is the probability of being missing is not dependent on the values of unobserved data, conditional on the observed values of the variables included in the analysis model. Imputation under MAR using chained equations following the guidance of White et al. will be undertaken.⁴ Variables in the imputation model will include the variables in the primary analysis model described above plus baseline WHO COVID-19 score (3 or 4), age (<65 or ≥65), receipt of dexamethasone and/or tociluzimab at the time of or prior to randomisation into MATIS. Additional auxiliary variables that are suspected to be associated with the outcome and are predictors of missingness will also be included. These are receipt of any effective treatments post randomisation as a result of co-enrolment when occurring postrandomisation, and receipt of known effective treatments dexamethasone and tociluzimab postrandomisation (>1 day post randomisation) and WHO COVID-19 scores at day 1 and day 7. Using White et al.'s rule of thumb we will impute m datasets based on the percentage of participants with incomplete outcomes, where m will be rounded to the nearest 10, for example if 8% of participants have incomplete primary outcome then m=10 will be used.

Before undertaking the multiple imputation as described above we will impute any missing baseline data deterministically only using other baseline data, this includes the baseline WHO COVID-19 status, age, receipt of dexamethasone and/or tociluzimab at the time of or prior to randomisation into MATIS. To do this we will impute missing values with the mean values of observed data. In line with White et al., outcomes will be imputed separately for each treatment group.

Imputed datasets will then be analysed using the primary analysis model described above.

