 FOS_{ij} : dummy variable for treatment ($FOS_{ij} = 0$ or 1) for participant i in jth site

 WHO_{ij}^0 : dummy variable for baseline WHO COVID-19 value for participant i in jth site (WHO_{ij})

0 or 1 where 0 indicates score of 3 and 1 indicates score of 4)

 AGE_{ij}^{0} : dummy variable for age-group ($AGE_{ij} = 0$ or 1 where 0 indicates <

65 years and 1 indicates \geq 65) for participant i

 DEX_{ij}^0 : dummy variable for receipt of dexamethasone at the time of or prior to randomisation (includes day of randomisation or one day post randomisation) ($DEX_{ij} = 0$ or 1) for participant i

 TOC_{ij}^0 : dummy variable for receipt of tociluzimab at the time of or prior to randomisation (includes

day of randomisation or one day post randomisation) ($TOC_{ij} = 0$ or 1) for participant i

 VAC_{ij}^0 : dummy variable for prior vaccination against COVID-19 at the time of or prior to randomisation (includes day of randomisation or one day post randomisation) ($VAC_{ij} = 0 \ or \ 1$) for participant i

 PAX_{ij}^0 : dummy variable for receipt of paxlovid at the time of or prior to randomisation (includes day of randomisation or one day post randomisation) ($PAX_{ij} = 0 \text{ or } 1$) for participant i

 MOL_{ij}^0 : dummy variable for receipt of molnupiravir at the time of or prior to randomisation (includes day of randomisation or one day post randomisation) ($MOL_{ij} = 0$ or 1) for participant i $Site_j$: dummy variable for each of the jth sites

 π_{ij} : probability of WHO COVID-19 \geq 5 for the ith participant in jth site

To account for missing outcomes in the primary analysis model we will impute missing WHO COVID-19 status using multiple imputation under the assumption of missing at random (MAR) as described in the primary statistical model at stage 1 section 3.1.2 plus the imputation model will contain the following additional variables: prior vaccination against COVID-19, and receipt of paxlovid and/or molnupiravir at the time of or prior to randomisation into MATIS, plus post-randomisation receipt of paxlovid and/or molnupiravir. Multiple imputation will be used for the final analysis regardless of levels of missingness at this stage.

As well as reporting odds ratios and 95% CIs, the model will be used to estimate the difference in proportion of participants with modified WHO COVID-19 Ordinal Score ≥ 5 .

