3.2.4 Length of stay

The time to discharge will be summarised by treatment arm using a Kaplan-Meier plot with extended at risk tables, detailing the numbers at risk, censored and discharged at each discrete time point, censoring at the day 28 visit. Withdrawals and deaths will be censored at the date of occurrence. In addition, summaries (means (SD) and median (IQR)) of length of stay will be tabulated amongst those that do not withdraw or die.

In addition, a Cox proportional hazards model will be used to estimate the hazard ratio of time to discharge between intervention arms with age (<65 or ≥65), site and receipt of known effective treatments dexamethasone and/or tociluzimab and vaccination status at the time of or prior to randomisation into MATIS included as covariates.

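### The event-free assumption for early discharge is not limited by destination, so a transfer or end-of-life discharge with no later data is scored as non-progression and never reaches the missing-data methods

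*Protocol*

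**What the plan says.** Protocol 3.3 counts an event when death, invasive ventilation, non-invasive ventilation or high-flow oxygen, or severe desaturation on high inspired oxygen occurs by day 14: "Specifically, the primary endpoint is met when the following are recorded within 14 days". Nothing there restricts where the event occurs.

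Protocol 4.2 then sets a default for patients who leave early: "discharge alive from the admitting hospital before 14 days will assume safety from the event". It is qualified at once: "in the absence of additional data confirming otherwise".

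SAP 3.1.2 restates the default with no qualifier: "For participants who are discharged early the assumption will be made that they did not progress to grade 5 WHO scale". The next sentence asks whether more than 5% of outcomes are missing once this has been done, so the default comes first and missingness is counted afterwards. For the final analysis, SAP 3.1.3 imputes "as described in the primary statistical model at stage 1 section 3.1.2", with extra variables in the imputation model.

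On follow-up after discharge, Protocol 3 describes patients who have recovered and are fit to leave: "Such patients will be followed up weekly with telephone monitoring until day 28 and additional blood test monitoring where practically possible". Protocol 9.1 and 9.2 set the end of data collection at the earliest of death, discharge and day 28, although 9.2 also invites discharged patients back weekly or has them telephoned. The footnote to Table 7 makes post-discharge visits optional. Among the data listed in 9.1 are inpatient or discharged status and the discharge date, but not the destination.

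**The concern.** Assuming no progression is reasonable for someone who has recovered and gone home. It is least credible for someone moved to another hospital, perhaps because they are worsening, or discharged to die elsewhere. On a literal reading, leaving the admitting hospital alive covers all three.

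Take a patient at grade 4 on day 3 who is moved to another hospital on day 4, with no further record. Under the rule the day-14 outcome is an observed non-event. Without the rule it would be missing and would be imputed.

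The scale makes this more pointed. Protocol 2.1 explains that a grade was added to capture deterioration in patients who are not offered escalation of organ support. Patients discharged for end-of-life care could well belong to that group.

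At stake are some true events in the primary outcome counted as successes, and an assumption that no planned analysis tests.

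**Working it through.** **1. Tracing one record.** For a patient transferred or discharged for end-of-life care before day 14, with no event before leaving and no later data:

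- Protocol 4.2: event-free. The exception does not apply because there are no contrary data.
- SAP 3.1.2: event-free, and not counted as missing.
- SAP 3.1.3: the final analysis uses the same imputation method, so the outcome is not imputed.
- Missing-data checks: the stage 1 extreme-case analyses (SAP 3.1.2) and the controlled imputation (Protocol 4.2) alter only missing outcomes, so they leave this record alone. The complete-case analysis keeps it as a non-event.

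**2. Reproducing the design power.** Inputs (Protocol 4.1): 50% versus 30%; 57 per arm at stage 1 and 152 in total; 5% missing; one-sided levels 0.25 and 0.027. Evaluable per arm: 57 × 0.95 ≈ 54 and 152 × 0.95 ≈ 144.

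For each stage, b = (d − z·s0)/s1, where d is the risk difference, s0 = √(2p̄(1−p̄)/n) and s1 = √([p0(1−p0) + p1(1−p1)]/n).

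- Stage 1: p̄ = 0.4, s0 = 0.0943, s1 = 0.0923, z = 0.6745, so b = (0.20 − 0.0636)/0.0923 = 1.478 and Φ(b) = 93.0% (plan: 92%).
- Final: s0 = 0.0577, s1 = 0.0565, z = 1.9268, so b = (0.20 − 0.1112)/0.0565 ≈ 1.57 and Φ(b) = 94.2%.
- Both stages: bivariate normal with correlation √(54/144) = 0.612 gives 89.4% (plan: 90%).

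The plan's figures reproduce.

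**3. Equal loss in all arms.** The documents give no number of transfers or palliative discharges. Let m be an assumed share of true events scored as non-events through the rule. The observed rate is the planned rate × (1 − m).

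| m | SOC | Drug | Risk difference | RR | OR | Power |
|---|---|---|---|---|---|---|
| 0% | 50% | 30% | 20 points | 0.6 | 0.43 | 89.4% |
| 2% | 49% | 29.4% | 19.6 | 0.6 | 0.43 | 88.5% |
| 5% | 47.5% | 28.5% | 19 | 0.6 | 0.44 | 86.9% |
| 10% | 45% | 27% | 18 | 0.6 | 0.45 | 84.1% |

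With 152 per arm, m = 5% to 10% means 152 × 0.5 × m = 3.8 to 7.6 SOC patients and 152 × 0.3 × m = 2.3 to 4.6 patients in a drug arm.

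**4. Loss in one active arm only.** Suppose no true effect, a true rate of 50%, 144 per arm, and the stage 1 rule ignored. For m = 5% the observed rates are 50% and 47.5%. Then s0 and s1 are both about 0.0589, b = (0.025 − 1.9268 × 0.0589)/0.0589 ≈ −1.50, and the chance of one-sided p < 0.027 is 6.6%. For m = 2% it is 3.9% and for m = 10% it is 14.0%, against 2.7% with no loss. This shows only that direction matters; nothing in the documents indicates such an imbalance.

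**The case against.** The strongest reply is that the rule is a default, not a verdict on everyone who leaves. The protocol's qualifier means that a known death, ventilation or severe desaturation by day 14 still counts. Deaths are to be recorded for all participants (Protocol 8.5), follow-up draws on notes, routine systems and registries (9.1), and SAP 3.1.2 promises every effort to obtain outcomes. A transfer for ventilation or ECMO would probably leave such a record. Elsewhere, discharge mostly means going home: Protocol 3, 7.16 and 9.2 and SAP 1.4.5 all speak of patients continuing treatment at home. Harm therefore needs several things together: a transfer or palliative exit coded as discharge, no event before leaving, an event afterwards, and no trace of it in any source.

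All of this stands, and it narrows the point. A reader might infer that anyone leaving alive is scored a success; the protocol's qualifier rules that out. A reader might also infer that transfers count as early discharges in the length-of-stay analysis. SAP 3.2.4 says only that "The time to discharge will be summarised by treatment arm using a Kaplan-Meier plot" and that deaths and withdrawals are censored; it is silent on transfers. Nor can a bias against the drugs be claimed: that would follow from equal proportional loss, which the documents do not establish.

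The reply does not remove the remaining gap. Usage elsewhere suggests going home but excludes nothing, no text requires day-14 status from a receiving hospital, and the SAP sentence lacks the qualifier.

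**Conclusion.** The concern holds for patients who are transferred or discharged for end-of-life care before day 14 and have no later data. They are scored as non-progressors, and no planned missing-data analysis examines that choice. Separately, the SAP omits the protocol's exception, so read literally it would not let later data overturn the assumption.

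The size is conditional. If the rule hid 5% to 10% of true events equally in all arms, power would fall by about 2.5 to 5 points, the odds ratio would move from 0.43 to 0.44 or 0.45, and the relative risk would not change. The 5% to 10% is an assumption, as is equal loss. Open-label treatment makes unequal discharge practice possible, but the documents do not show it, so neither the frequency nor the direction of bias can be settled from them.

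**What to change.** - In Protocol 4.2 and SAP 3.1.2, apply the event-free assumption only to discharge alive to home or usual residence.
- Carry the protocol's exception into SAP 3.1.2, and say in 3.1.3 that it holds for the final analysis.
- For transfers and end-of-life discharges, obtain day-14 status from the sources that Protocol 9.1 already names. If it remains unknown, treat the outcome as missing and impute it, so that the planned sensitivity analyses cover it.
- In SAP 3.2.4, state as a clarification that transfer to another acute hospital is not discharge.

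The cost is a few sentences and one data item. Destination is not listed in Protocol 9.1, so it must be added to the case report form or retrieved from notes. Slightly more outcomes will be imputed.

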#### 4.3 DATA MANAGEMENT AND RETENTION

Clinical research teams will use the bespoke study web-based applications for study management and to record participant data (including case report forms) in accordance with the protocol. Data will be held in central databases located at the CCO or on secure cloud servers. In some circumstances (e.g. where there is difficulty accessing the internet or necessary IT equipment), paper case report forms may be required with subsequent data entry by either LCC or CCO staff. Although data entry should be mindful of the desire to maintain integrity and audit trails, in the circumstances of this epidemic, the priority is on the timely entry of data that is sufficient to support reliable analysis and interpretation about treatment effects. CCO staff will be responsible for provision of the relevant web-based applications and for generation of data extracts for analyses.

All data access will be controlled by unique usernames and passwords, and any changes to data will require the user to enter their username and password as an electronic signature in accordance with regulatory requirements. Staff will have access restricted to the functionality and data that are appropriate for their role in the study.

[figure not shown]
#### **Data retention**

Data and all appropriate documentation will be securely archived for a minimum of 10 years after the completion of the study, including the follow-up period in accordance with College policy

## 5 PARTICIPANT ENTRY

#### 5.1 PATIENT SELECTION

In hospital, potential participants will be identified through hospital workers upon presentation at recruiting sites and through public health agencies

#### 5.2 INCLUSION CRITERIA

- Patients age ≥ 18 years at screening
- Patients meeting criteria of:
  - Hospitalization AND
  - SARS-CoV2 infection (clinically suspected\* or laboratory confirmed) AND
  - o Radiological change consistent with COVID-19 disease
- Mild or moderate (Grade 3 or 4 severity by modified WHO COVID-19 Ordinal Scale) C19 pneumonia
- CRP ≥ 30mg/L at any time point
- Informed consent from patient or personal or professional representative
- No medical history that might, in the opinion of the responsible clinician, put the patient at significant risk if he/she were to participate in the trial
- Agreement to abstain from sexual intercourse or use contraception that is >99% effective for all participants of childbearing potential for 42 days†
- For male participants, agreement to abstain from sperm donation for 42 days after the last dose of study drug ‡
- Non-English speakers will be able to join the study. If patients are unable to understand verbal or written information in English - hospital translation services will be requested at the participating site for the participant where possible
- Patients normally on non-invasive ventilation such as continuous positive airway pressure (CPAP) at home are eligible

#### 5.3 EXCLUSION CRITERIA

• Requiring either invasive or non-invasive ventilation including CPAP or high flow nasal oxygen at any point

MATIS version 4.0 dated 2nd November 2022

IRAS: 282552 Page **30** of **57** 

\* Clinical suspicion of COVID-19 pneumonia will be confirmed by two independent clinicians.

<sup>† Females must be either post-menopausal for at least 1 year or surgically sterile; or if female of child-bearing potential, must not be pregnant or lactating and must agree to use an acceptable method of birth control throughout the duration of the trial and for 30 days following the last dose. Acceptable methods of birth control are defined as: hormonal contraception (pill, injection or implant) used consistently for at least 30 days prior to enrolment, intrauterine device (IUD), double-barrier (ie, condom and spermicide, or condom and diaphragm), or true abstinence (when this is in line with the preferred and usual lifestyle of the subject).

<sup>‡ Male subject with a partner of childbearing potential must agree to use an appropriate double-barrier method of contraception during the time interval between administration of the first dose of study drug and 30 days following the last dose, or must agree to true abstinence (when this is in line with the preferred and usual lifestyle of the subject).

after hospital admission and before baseline not related to a pre-existing condition (e.g. obstructive sleep apnoea)

- Grade ≥ 5 severity on the WHO COVID-19 Ordinal Scale
- O₂ saturation < 90% on ≥ 60% inspired oxygen at baseline

- In the opinion of the investigator, progression to death is inevitable within the next 24 hours, irrespective of the provision of therapy
- Any medical condition or concomitant medication that in the opinion of the investigator would compromise subjects' safety or compliance with study procedures.
- Any medical condition which in the opinion of the principal investigator would compromise the scientific integrity of the study
- Known severe allergic reactions to the investigational agents
- Use of drugs within the preceding 14 days that are known to interact with any study treatment (FOS or RUX), as listed in the Summary of Product Characteristics
- Child Pugh B or C grade hepatic dysfunction
- Pregnant or breast feeding

